## **M. Technology: Zoom Information**

### **1. Computers and other equipment**

- a. Study staff are in charge of transporting computers, tablets, headsets, extension cords from storage to the lab
- b. All equipment needs to be tested prior to the beginning of the SP session
- c. Videos need to be stored on the external hard drive after the SP session has ended.
- d. All equipment needs to be locked up immediately after the end of the SP session

### **2. Recording of videos:**

The SP encounters will be recorded via Zoom using 6 computers and headsets.

30 minutes before students start the SP exercise, computers will be placed on the table and connected to the internet for zoom meetings by the IT person.

- a. The IT person will make sure headsets are plugged into the computers and that all computers are plugged into power outlets and are charging.
- b. The IT person will make sure that Zoom is working properly on all the computers by turning Zoom on and recording a short test video.
- c. IT person is in charge of making sure all SPs are recording their Zoom session
- d. The project coordinator is in charge of making sure that all recorded Zoom sessions are saved on Box.com

### **3. Zoom procedures during the pilot:**

- a. Use speaker view during the interview
- b. Be aware of the position of the camera
- c. Be aware of lighting
- d. Make sure you are not muted
- e. Make sure the recording light is on - this is very important

## **N. Administration of the Follow-up**

This follow-up protocol is to be revised in November 2021, based on the experience of conducting the baseline assessment.

There are four main tasks to think about during the period between baseline and follow-up. They are:

1. Avoidance of bias
2. Minimization of dropout
3. Administration of the follow-up survey
4. Administration of the follow-up SP assessment
5. Giving the Control participants the opportunity to attend the seminar (**September 2022**).

### **1. Avoidance of Bias**

It is critical for the follow-up that participants in both arms of the trial be treated in the same way. Given that some participants may complete the SP assessment and others in May, it will be important to

randomize treatment and control arm participants so that both groups, on average, complete the follow-up assessment at the same time and under the same conditions.

As there is no reason for the SPs and the staff to know what arm of the study the participant was in, all study staff and SPs should be kept blind to this knowledge.

## 2. Minimization of Drop Out

- a. Participants in both arms of the trial are easily followed up since they are enrolled students at MUHAS. At enrollment, students will be asked to supply a mobile number to contact them in case they need to. Should a participating student not keep their pre-test or 3-month follow-up appointment, every effort will be made to facilitate another session for them to complete study tasks. Participant attendance at the seminar is monitored.
- b. If a participant leaves MUHAS and is no longer considered a student, they can remain a participant in the study and so can participate in the follow-up portion of the study. **Project Coordinator** is the staff person who shall discuss with the participant the reason why they are no longer a student and may include or exclude the student from further participation (as appropriate).
- c. **Project Coordinator** will keep a log of any students who inform the study that they wish to no longer participate. This study is voluntary so a participant may choose to leave the study at any time. **Project Coordinator** shall ask them for any reasons for withdrawal.
- d. Also, he will follow up with any participant who completed the baseline assessment but failed to complete the follow-up. Every effort will be made to facilitate the student completing the follow-up. Should he encounter participants who “disappear” from the study (i.e., they enrolled in the study and completed the baseline but then were not contactable for follow-up, he will check with MUHAS administration and the relevant school whether the participant is still a current student, and if not, the reason why. Given the COVID epidemic, he will log the reason given why the participant is no longer a student (e.g., illness or death at the time of follow-up).

## 3. Administration of the Follow-up Survey

**Objective:** The purpose of the final survey is to collect information on student's knowledge, attitudes, and self-evaluation of skills related to sexual health at least 3 months after the baseline assessment. To ensure all participants are treated equally, to reduce participant burden, and for ease of administration, the follow-up survey will be completed online by all participants at the same time.

### Procedure

- a. Prior to the survey being sent to participants, **Project Coordinator** is responsible for pre-piloting the survey with internal staff to ensure that all questions are being asked and that the survey is free of bugs.
- b. **Researcher 3** is in charge of overseeing the final survey completion. Before sending out the link to the survey, they will check that the Internet is working well. If it is problematic, **Researcher 3** may delay sending out the email until the Internet is working.
- c. In December (i.e., 24 hours before the first follow-up SP assessment) **Researcher 3** will send out an email and/or text to all participants (i.e., both those in the intervention and the control conditions) with a link to the survey. The participants are asked to complete this follow-up survey within 7 days. All instructions on the survey should mirror those on the baseline survey with the following differences. It will be noted that completing both the survey and the SP follow-up assessment is needed to receive compensation. The link will provide a phone number and email in case a participant has questions or difficulties. And participants will be asked to complete this by themselves without asking anyone else answers to any question.

- d. Each participant is instructed to complete the online using their phone, laptop, computer, or other online devices at a time and place convenient to them.
- e. **Project Coordinator** will monitor the completion rate of surveys on a daily basis. Monitoring involves checking the surveys that have been completed (to ensure they are complete then sending a thank you email to those who have completed that they did so).
- f. **Minimization of Attrition Protocol:** All participants who have not completed the follow-up survey within 7 days will be sent an email and/or text reminder at 7-days asking them to complete it within 48 hours. Two days later, anyone who has not completed the survey receives a second email and/or text asking them to complete it within 48 hours. Those who have not completed it after the second reminder then receive a personalized phone call asking them to complete it within the next 48 hours.
- g. The goal is to have everyone complete the follow-up surveys. During the two weeks devoted to the administration of the follow-up survey, **Project Coordinator** will give regular updates on the number and percent of participants who have completed the follow-up survey.
- h. **Project Accountant** is in charge of the payments which will be approximately \$25 for completion of both the SP assessment and the online follow-up survey. There is no partial payment for completing only one or these two activities.

#### **4. Administration of the Follow-up SP Assessment (five critical steps to follow)**

**Objective:** The administration of the follow-up should be conducted in a way that reflects a high standard and replicates as much as possible the methods used for the baseline assessment.

There are 5 critical tasks that need to be completed at the follow-up assessment. They are:

- i. Ensure the SP evaluation is completed with no bias
- ii. Ensure only healthy students, staff and SPs enter the study area.
- iii. Completion of the follow-up SP evaluation
- iv. Payment of the participants for completing the baseline assessment.
- v. Wait-listing the control participants for the 2022 seminar.

Ideally, a total of 412 participants are expected to move through a 90-minute session that involves two SP simulations involving a simulated patient (SP) presenting with a sexual health problem (15 min. each).

**Staffing:** In addition to **Project Coordinator**, we need staff members to (a) supervise the SP; (b) provide the participant payment, and (c) wait-list those from the waitlist control condition who wish to participate in the 2022 training.

##### ***a. Ensure the SP evaluation is completed with no bias***

The goal is to have every participant complete the follow-up SP assessment with the SPs (and ideally staff) blind to whether the participant was in the intervention or control arms. Care should be taken so that both intervention and control arms are treated equally. This means that intervention and control arm participants should complete the follow-up assessment at the same time.

If the SP assessment has to be spread over two months (e.g., January and May) it is critical that equal numbers of intervention and control arm participants complete it in January, with the rest completing it in May.

##### ***b. Ensure only healthy students, staff and SPs enter the study area.***

As per the COVID protocol (see below), all students, staff, and SPs will have the temperature taken and are required to wear masks while completing the final assessment. A student, staff, or SP with a temperature will activate the COVID protocol.

### **c. SP Simulation Lab**

**Control center:** This is a table from which investigators will run the simulations. The table is located in the lab.

- i. **Researcher 1** is in charge of running the simulation lab.
- ii. The “control center” will be a table and several chairs located in an easily accessible location in the simulation laboratory.
- iii. All supplies and equipment will be stored/or placed in this area. All paperwork will be kept in the control center for easy access.
- iv. At least 1 staff member will always be at the control center to answer questions that students or SPs may have and to troubleshoot any problems.
- v. The control center will be maintained throughout the day and kept clean and organized.
- vi. At the end of the day during the interventions and training, all materials used for the study will be stored for the full trial use.
- vii. We have planned to have 12 simulations running concurrently in 4 rooms. Each room will have the 3 SPs with the same case. The student waits outside the room until called, then enters the room and completes the case. When the student has completed the case they are directed to the next room to complete their second case. So, the first student completes Case A (in-room A) and then goes to Room B to complete case B. The second student goes to Room C to complete Case C and then Room D to complete Case D. The third student goes to Room A (to complete A&B), while the 4th student is sent to Room C (to complete Case C and then to Room D to complete Case D).
- viii. SP and learners arrangement: Each participant will complete two SP cases of about 15 minutes each; i.e., 30-40 minutes in total.

Participants (learners and SP) will spend 20 minutes at each station.

#### ***Breakdown of 20 minutes:***

- Five minutes will be spent in the introduction of the case at each station.
- 10 minutes will be used during the discussion/history taking
- Each participant (learner and SP) will be required to fill in a survey/checklist before moving to the next station which will take about 5 minutes.

**Dr. X** will be responsible for assigning learners to different stations. SP will not move/leave their station, they will remain in the original station. Between sessions, participants will be given snacks and bathroom breaks. **Dr. X** will keep time and address any concerns or questions as they may arise.

### **d. Setting up a simulation scenario:**

The following are the steps that SPs will take when setting up for a scenario:

Sit on the appropriate chair

Turn on the computer

- i. Open Zoom
- ii. Wait for the student to arrive and sit down
- iii. Press the “record” button ← Very important
- iv. Play role as SP
- v. Watch for the “1 minute left” warning sign
- vi. Once 10 minutes are over, end the conversation with a student
- vii. Press the “stop recording” button
- viii. Wait for the next student to arrive
- ix. Repeat process

At the end of the simulation, the student is informed to return **to Dr. X** and to provide her with their completed simulation forms. Each student should hand two forms to her. **Dr. X** checks the form and sends the student to the baseline survey station.

*e. Payment and Feedback*

- a. **Project Accountant** is the person in charge of payments.
- b. **Project Coordinator** reviews with the student that they have completed the two SP assessments and checks that the survey responses have been captured in qualities.
- c. **Project Accountant** then hands them the payment for completing the assessment.
- d. Finally, **Project Coordinator** asks each participant if they have any other questions or any feedback about their experience in the trial.
- e. For students who provide feedback, **Project Coordinator** logs this information for discussion at the team meeting.
- f. Whenever problems are identified and are immediate and easily fixed, **Project Coordinator** is authorized to modify study procedures to improve the student experience.

*f. Waitlist: Being waitlisted for the September 2022 seminar*

- a. **Project Coordinator** will ask all control arm participants once they have been paid if they wish to be waitlisted for the September 2022 training. He shall also extend this invitation to any participant assigned to the intervention arm who was not able to attend the training (e.g., because of illness). Because of limited resources, students who completed the training in 2021 will not be allowed to repeat it in 2022.
- b. Project Coordinator will explain to each participant that the training in 2022 will occur if sufficient students register and confirm in July 2022. Project Coordinator will hand each person who wishes to be on the waitlist a one-page flyer detailing the likely dates of the seminar, and ways to contact the study.
- c. **Project Coordinator** will review and update contact information for any student who is waitlisted for the seminar.

NCT03923582

R01HD092655

Title: Training for Health Professionals

Statistical Analysis Plan

Last updated: December 1, 2023

The intervention effect will be evaluated using a multiple regression analysis. The intervention group was assessed at baseline, immediately post-intervention, and follow-up, while the control group was assessed at baseline and follow-up only. Thus, difference scores (follow-up – baseline) will be calculated for each outcome listed above and used as the outcome for the regression models. "Intervention" (dummy coded as 0=control, 1=intervention) will be the primary predictor in the model. To assess whether there is a differential effect of intervention based on demographics, students' discipline, gender, and religious affiliation will be included as interaction effects (full model). In the current study, we recruited nursing, midwifery, and medical students. Due to the small number of midwifery students, midwives will be grouped with nurses for modeling purposes. Thus, discipline will be recoded into a variable called "Nursing" (0=medicine, 1=nurse/midwife). Similarly, gender will be coded as "Female" (0=male, 1=female) and religion will be coded as "Muslim" (0=Christian, 1=Muslim), based on the demographic groups with the most responses (demographic information was collected at baseline). If the interaction effects between Nursing, Female, and Muslim with Intervention are not statistically significant, the interactions will be removed from the model and the reduced model (without interaction effects but still including the main effects) will be fit and interpreted. All analyses will be run using R software (v 4.2.1).

Of the 412 recruited, one participant did not complete the post-intervention survey and three participants did not complete the three-month follow-up. Thus, these four participants will be removed from analysis. Furthermore, if participants did not identify as male/female or Christian/Muslim (e.g., responded "Other" or "Prefer Not to Answer"), they will be considered missing data and removed from analysis. Based on the demographic information collected at baseline, this will result in 396 participants for statistical modeling (96% of the total sample).

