## **9. Randomization of Participants to Study Arms**

**Objective:** The purpose of the randomization is to assign students to the intervention or control group arms of the trial in a way that is fair and is seen by the participants to be fair. It is also done to prevent students from trying to change their assignment from one group to the other.

We will use a block randomization for each group (midwifery, nursing and medical students), batch (in groups of ten) randomization process. Once students have completed the baseline SP and survey, they will receive their assignment in an envelope.

For logistical reasons, the students are randomized after undertaking the baseline assessment. To prevent several threats to study validity, the students and staff should not be told a student's assignment to the intervention arm or the control arm until after they have completed the baseline assessment.

- a. **Researcher 2 and Researcher 3** are in charge of the randomization.
- b. **Researcher 3** will keep three envelopes titled "midwifery", "nursing", and "medical student" envelopes. Inside these envelopes at the start of each cycle are 10 pieces of paper, all the same size. Five pieces of paper will have the word "2021" on them and five will have "2022."
- c. **Researcher 3** draws a piece of paper with 2021 on it, they will record the student who will be attending the training in 2021 (i.e., next week). If s/he draws a piece of paper with 2022 on it, they will be recording the student as eligible to attend the training in 2022.
- d. **Batch Randomization:** Once a piece of paper is drawn, it is NOT returned to the envelope but instead put in the "used envelope" for reuse later. So, when the first medical student is to be randomized, **Researcher 3** draws from the medical students' envelope with 10 pieces of paper in it; for the second, they draw from the envelope which now has 9 pieces of paper in it, and so forth. When the envelope has no more pieces of paper left in it, the envelope is refilled so it has 5 2021 and 5 2022 pieces of paper.
- e. **Researcher 3** then records the randomization on a master list of students.
- f. **Note:** Staff involved in the randomization should avoid using the terms "intervention" and "control" groups. Instead, we use the term, the training happening next week or the training for next year.

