### **4. SP Simulation Lab i.e., arrangement and setting**

This is a table from which investigators will run the simulations. The table is located in the lab.

- i. **Dr. X** is in charge of running the simulation lab.
- ii. The "control center" will be a table and several chairs located in an easily accessible location in the simulation laboratory.
- iii. All supplies and equipment will be stored/or placed in this area. All paperwork will be kept in the control center for easy access.
- iv. At least 1 staff member will always be at the control center to answer questions that students or SPs may have and to troubleshoot any problems.
- v. The control center will be maintained throughout the day and kept clean and organized.
- vi. At the end of the day during the interventions and training, all materials used for the study will be stored for the full trial use.
- vii. We have planned to have 12 simulations running concurrently in 4 rooms. Each room will have the 3 SPs with the same case. The student waits outside the room until called,

then enters the room and completes the case. When the student has completed the case they are directed to the next room to complete their second case. So, the first student completes Case A (in-room A) and then goes to Room B to complete case B. The second student goes to Room C to complete Case C and then Room D to complete Case D. The third student goes to Room A (to complete A&B), while the 4th student is sent to Room C (to complete Case C and then to Room D to complete Case D). In this way, half of the students end up completing Case A&B at baseline and half these cases at follow-up.

viii. [name] (or the person at the table) will log whether the student was assigned to cases AB or cases CD before sending them to the room. She supervises each student putting their ID number on each form.

**SP and learner's arrangement:** Each participant will complete two SP cases of about 15 minutes each, i.e., 30-40 minutes in total.

Case A: Woman who has been sexually assaulted (see **Rehema scenario**)(20 minutes)  
 Case B: Man with erectile dysfunction and homosexual history (20 minutes)  
 Case C: 16-year-old girl is worried about getting pregnant by her sugar daddy (case has been developed, see **Aliyah Scenario**) (20 minutes)  
 Case D: Young man with a drip (urethral discharge) and groin pain (case has been developed, see **Emmanuel scenario**) (20 minutes)

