#### 4. **Video Data for RCT**

A 3,296 video clips (412 participants x 4 videos x 2 admins) will each be assigned a unique code number matched to a master database. All videos are uploaded into the database and stored at two sites in Tanzania. Video data will also be saved to the BOX cloud at the end of each day.

- a. Project Coordinator is the data manager for the videos which will be saved in password-protected files. Since the videos contain identifying information (faces), he will allow access to the videos on an as necessary basis.
- b. **Rating: Drs. Y and X** will oversee the rating of videos.
- c. Videos are randomized so raters are blind to participant condition assignment (intervention or control) and blind to whether the assessment is pretest or posttest.
- d. No videos are reviewed by the expert raters until all the videos have been completed.
- e. On the rating form, the rater begins the review by writing out the Student ID, the three-digit Case-SP number (as reported on the video), and their assigned rater ID.
- f. Once the raters have rated all the videos their ratings are sent to **analyst**. **Study analyst** has the key to the blind and so can identify for each student, which are the two baseline videos and which are the two follow-up videos.

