#### 5. **Primary Dependent Variables.**

The following are the primary dependent variables:

- a. Knowledge is assessed using the 12-item knowledge quiz that is tailored to assess knowledge items taught in the curriculum.
- b. Attitude change: is from the SHEPS attitude/comfort scale
- c. Clinical skills are assessed using the clinical/expert raters review of the SP videos. See <https://link.springer.com/content/pdf/10.1023/A:1009878124073.pdf>.

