#### **5. Procedures for minimizing face to face contact**

- a. The day before their participation, participants will receive an email reminder confirming their participation and details of where to meet and COVID-19 measures to follow.
- b. On the day of the study, participants will be staggered to minimize the number of persons arriving at any one time.
  - i. The participants arrive at the welcome desk where their temperature is taken and handwashing is observed.
  - ii. Then, they first read a welcome overview of the study and review the consent form, and if comfortable, sign it.
  - iii. Each person will be given a pen and pencil for them to keep so there is no sharing of writing instruments.
  - iv. After this, they are sent to the “lab” where they are videoed taking three sexual histories.
  - v. Only 6 students will be allowed in the lab at any one time (with 2 staff members and 1 IT person present). Each station has a laptop and headphones and will be at least 6 feet from another station.
  - vi. In addition, we have purchased dividing screens both to promote privacy and to prevent COVID-19 transmission, so each person will have their own “cube”.
- c. During the 44 days of the curriculum, the student participants are given a contact email and phone (of a faculty licensed health professional) so that if they feel ill or develop a temperature outside of when the intervention is occurring, they can inform the study. Anyone reporting symptoms will be encouraged not to continue participation but instead, to prioritize their health.

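### The SAP analyses raw change scores without each outcome's own baseline score, which gives up precision unless the true baseline slope is 1

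*SAP*

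**What the plan says.** The SAP's first paragraph takes follow-up minus baseline differences, which "will be calculated for each outcome listed above and used as the outcome for the regression models". Arm is the main predictor. The full model adds Nursing, Female and Muslim with their interactions with arm. If the interactions are not significant they are dropped and the main effects stay. The only baseline information in either model is demographic. The reason given for difference scores is that controls had no immediate post-training assessment.

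Protocol section C.9 says that "the students are randomized after undertaking the baseline assessment", and section G.5 (item j) withholds randomisation until the baseline survey is complete. Section I.5 names three primary dependent variables: a 12-item knowledge quiz, the SHEPS attitude/comfort scale, and skills, of which it says "Clinical skills are assessed using the clinical/expert raters review of the SP videos". It gives no analysis model, so the protocol does not supply the missing covariate.

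The SAP is dated December 1, 2023. Its second paragraph already reports that "three participants did not complete the three-month follow-up" and gives an analysis set of 396 of 412.

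**The concern.** Subtracting baseline is the same as adjusting for it with a slope fixed at 1. The data can estimate that slope, and it need not be 1. Where it is not, the change score carries residual noise that an adjusted model removes. The stated reason for difference scores explains why the post-training assessment is left out. It does not explain leaving out baseline, because both arms have baseline and follow-up.

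At stake are wider confidence intervals and lower power for each outcome. The same noise enters the interaction tests, whose significance decides which model is interpreted. In any one trial the loss appears as sensitivity to chance imbalance: if the arms differ by d at baseline, the change-score estimate moves by −(1 − b) × d, while the adjusted estimate does not.

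**Working it through.** **The plan's own figures.** Neither document states a power calculation, effect size, SD, correlation or alpha, so there is no design figure to reproduce. The one checkable figure agrees: 396/412 = 96.1%, stated as 96%.

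**Inputs**
- n = 396 (SAP, second paragraph). About 198 per arm is assumed from the 1:1 blocks of ten in Protocol C.9.
- r, the within-arm correlation of baseline and follow-up given Nursing, Female and Muslim: assumed.
- k = SD(follow-up)/SD(baseline): assumed. Both r and k are taken as equal in the two arms.
- b = r × k, the true baseline slope.

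**Formulas**, in units of the baseline variance:
- Var(change) = 1 + k² − 2rk
- Var(adjusted) = k²(1 − r²)
- Difference = (1 − rk)² = (1 − b)²

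Example, r = 0.5 and k = 1: 1 + 1 − 1 = 1.00 against 0.75. The difference is 0.25 = (1 − 0.5)² and the ratio is 1.333.

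| r | k | b | Variance ratio, change/adjusted | SE ratio | 396 ÷ ratio |
|---|---|---|---|---|---|
| 0.3 | 1 | 0.30 | 1.538 | 1.24 | 257 |
| 0.5 | 1 | 0.50 | 1.333 | 1.15 | 297 |
| 0.7 | 1 | 0.70 | 1.176 | 1.08 | 337 |
| 0.8 | 1 | 0.80 | 1.111 | 1.05 | 356 |
| 0.9 | 1 | 0.90 | 1.053 | 1.03 | 376 |
| 0.5 | 0.8 | 0.40 | 1.750 | 1.32 | 226 |
| 0.5 | 1.25 | 0.625 | 1.120 | 1.06 | 354 |
| 0.5 | 1.5 | 0.75 | 1.037 | 1.02 | 382 |
| 0.8 | 1.25 | 1.00 | 1.000 | 1.00 | 396 |

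The loss occurs on both sides of 1: at r = 0.9 and k = 1.5, b = 1.35 and the variances are 0.550 and 0.4275.

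**Against ignoring baseline.** Var(change) − Var(follow-up) = 1 − 2b, which is positive when b is below 0.5. In that range the change score is less precise than using follow-up alone.

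**Power.** Take an effect that the adjusted model detects with 80% power (198 per arm, two-sided 0.05 assumed). With equal SDs, the change-score model has about 62%, 68%, 73% and 78% power at r = 0.3, 0.5, 0.7 and 0.9.

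**Chance imbalance.** The SE of the baseline difference is √(2/198) = 0.1005 baseline SD. At b = 0.5, a one-SE imbalance shifts the change-score estimate by 0.5 × 0.1005 = 0.050 SD.

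**Simulation.** At n = 396 with three binary covariates and 4,000 trials per setting, the variance ratios were 1.52, 1.30, 1.14 and 1.11 at r = 0.3, 0.5, 0.7 and 0.8 with k = 1, and 1.00 at r = 0.8 and k = 1.25. These are close to the formula. With baseline in the model, follow-up and change as outcome gave the same treatment estimate, apart from rounding of about 1e-15.

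**The case against.** The strongest reply is that this is a matter of efficiency and not an error. The planned model is explicit, reproducible and unbiased under randomisation, and with no power target in the documents no design claim is shown to fail. That is right, and it limits the point to precision.

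The size is also wholly assumed. At r = 0.9 with equal SDs the excess variance is only 5%. At an SD ratio of 1.25 it is 6% at r = 0.6 and 2% at r = 0.7. A quiz on taught content might compress at the top in the trained arm, so that r and the SDs differ between arms. This stands: the documents cannot separate a small loss from a large one. The direction does not depend on these values, because in large samples with 1:1 allocation the change score never beats adjustment.

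The imbalance shift is not a second harm. Its variance over randomisations, (1 − b)² × Var(d), is exactly the excess variance already counted. This also stands.

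On timing, the SAP postdates the planned follow-up and already reports attrition, so replacing the main model now could be a post hoc choice. That affects how the adjusted result is labelled, not whether it is worth having.

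Finally, waitlisted students may enter the intervention arm without being randomised (Protocol C.9, item h). That affects both models and does not favour change scores.

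**Conclusion.** The concern holds. The outcome's own baseline score is missing from both models, it is collected before randomisation, and leaving it out costs precision unless b = 1. With equal SDs and r from 0.3 to 0.8, the excess variance runs from 54% down to 11%, and the SE is 24% down to 5% larger. Across SD ratios of 0.8 to 1.5 at r = 0.5 it runs from 75% down to 4%, and at r = 0.8 with ratio 1.25 it is zero. These figures assume the stated r and k, a common r and k in both arms, and about 198 per arm.

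The algebra is certain; how much it matters here cannot be determined from the documents. Two further limits apply to clinical skills. That the SAP's outcomes include them is an inference, because no list stands above its reference to one, and the SAP does not say whether the 396 applies to video-rated outcomes.

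**What to change.** Add each outcome's own baseline score as a covariate in both the full and the reduced model. The treatment estimate is then the same whether follow-up or change is the dependent variable, so change scores can still be reported.

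Record the date of the change and whether any results had been seen. If they had, report the adjusted model beside the planned one and label it as added later.

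For clinical skills, first reconcile how many and which cases each student took at each visit:
- Protocol G.4 (item vii) plans two cases per visit with a swap, so that "half of the students end up completing Case A&B at baseline and half these cases at follow-up".
- N.4.c repeats the two-case routing at follow-up without stating the swap.
- K.5 has students "videoed taking three sexual histories".
- I.4 counts "412 participants x 4 videos x 2 admins", or 3,296 clips, where two cases at each of two visits give 412 × 2 × 2 = 1,648.

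If the swap was carried out, also add the case pair as a covariate. It can be taken from the control-table log (G.4, item viii) and the case number on the rating form (I.4, item e).

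The main change costs one SAP sentence, a dated note and one degree of freedom per model. If the true slope is exactly 1, the price is about 0.3% more variance at n = 396. The case-pair term costs one more degree of freedom for the skills model, plus the work of linking the log to the ratings. No new data are needed.
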